#### 3 Background and rationale

#### 3.1 The medical problem

Cancer is often characterized by extensive invasion, early metastases, and, in many cases, a rapidly occurring marked cachexia leading to a very limited prognosis especially in the metastatic situation.

Cachexia is a strong and independent predictor of mortality, poor therapeutic response, diminished functional capacity, and reduced quality of life (QoL). It is defined as the debilitating state of involuntary weight loss, often connected with anorexia, tissue wasting, malnutrition, and inability for natural nutrition intake. The combination of these symptoms, also characterized by systemic inflammation, is also named "cancer anorexia-cachexia syndrome" (CC) [Vanhoutte et al., 2016; Fearon et. al, 2011]. The most important phenotypic feature is muscle wasting and functional impairment as a result of increased protein degradation and reduced protein synthesis or both [Bossola et al., 2007]. The syndrome is life-threatening and debilitating for approximately 50% of all cancer subjects [Bossola et al., 2007].

As reported, the QoL is significantly impaired in CC subjects and there is evidence for increased morbidity and mortality of subjects with CC [Bossola et al., 2007]. Subjects suffering from CC commonly have derangements in basal metabolic rate as well as reduced appetite and food intake. Even moderate weight loss is associated with psychological stress and lower QoL. Furthermore, CC affects subject's response to chemotherapy [Bossola et al., 2007].

Malnourished patients are more difficult to guide through chemotherapy experiencing more severe side effects resulting in progressive cachexia. The outcomes of subjects with CC receiving chemotherapy can be improved with nutritional intervention (NI) [Bauer and Capra, 2005]. Supplementation with parenteral nutrition (PN) improves the QoL in subjects with advanced CC. There is also data indicating that NI has a synergistic effect with anti-cancer

-CONFIDENTIAL- Page 7 of 33

therapy and results in better clinical outcome [Ravasco et al., 2005a; Ravasco et al., 2005b; Bauer and Capra, 2005; Caccialanza R. et al., 2018].

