#### 4 Study design

This is an open-label, randomized, multicenter, investigator-initiated, phase IV trial. A total number of 216 patients will be enrolled (see chapter 7 for statistical calculations).

Patients with metastatic or localized solid tumors who fulfil the eligibility criteria and who have an indication for parenteral nutrition will be enrolled.

Patients will be stratified according to ECOG (0-1 vs. 2 vs. 3), the modified Glasgow Prognostic Score (mGPS) (0-1 vs. 2) and whether the patient receives concurrent systemic anti-cancer treatment (e.g. chemotherapy, targeted therapy, immunotherapy) or not.

In a first step, patients will be randomized in a 2:1 ratio to Arm A or Arm B:

Arm A: Standard Parenteral Nutrition using Eurotubes®.

or

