#### 5.2.2 Secondary endpoints

#### Efficacy endpoints

- Relative weight change determined at baseline and during study visits approx. every four weeks after enrolment;
- Relative change of albumin and CRP levels measured at baseline and during regular study visits;
- Overall survival (OS) defined as the time from randomization to death from any cause.

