#### 6.3.2 Statistical methods for the analysis

#### Patient Demographics/Other Baseline Characteristics

The following demographic and baseline characteristics will be summarized descriptively by treatment group:

- Gender and age;
- Patients' disease (e.g. colon cancer, breast cancer, gastric cancer);
- Tumor status (localized or metastatic solid tumors);
- Number and type of organs involved in metastatic disease (e.g. liver, lung, lymph nodes, bone);
- Patients history (concomitant disease, number and type of previous anti-cancer therapies);
- Type and start date of the current/concomitant anti-cancer therapy;
- ECOG performance status;
- mGPS
- Nutrition risk screening score;
- Baseline lab values and baseline QoL;
- Other characteristics.
- Type of central catheter used for parenteral nutrition

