#### Secondary Endpoints

All secondary analyses, excluding safety endpoints analyses, which will be based on the safety population, and the CRI, which will be based on the per protocol population, will be based on the ITT population. Sensitivity analysis of the primary endpoint and other important endpoints will be performed in the per protocol population, also. The parameters will be evaluated in an explorative manner, providing means, medians, ranges, standard deviations and/or confidence intervals. Rates will be compared using fisher's exact test and continuous variables using t-test. For the time-to-event variable OS, the Kaplan-Meier method will be used, and treatment groups will be compared using a log rank test. All resulting p-values for secondary endpoints will be considered descriptive and will be presented explicitly without referring to hypotheses or a significance level. Usually, no p-value adjustment for multiple-testing will be performed. Thus, the p-values will reflect the comparison-wise error and not the experiment-wise error. All p-values will be two-sided if not stated otherwise. The statistical methods described in this section are suited for the data and distributions usually expected in this type of trials. The suitability will be checked and if necessary, the statistical method will be modified accordingly, with critical discussion of the original and modified results.

Further details of the planned procedures and specific analyses will be defined in the statistical analysis plan, latest prior to locking the database.

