#### 7 Patient Selection

#### 7.1 Inclusion Criteria

Patients\* must meet the following criteria to be eligible for the study:

- 1. Age  $\geq$  18 years
- 2. Histologically confirmed metastatic or localized solid tumor. Perioperative setting of HPN is allowed if HPN is planned for a duration of  $\geq 2$  months
- 3. ECOG performance status of 0, 1, 2 or 3
- 4. Indication for PN (the subject needs a PN independent of the trial)
- 5. PN planned for 3 or more days per week
- 6. Negative pregnancy test in women of childbearing potential
- 7. Willingness to perform double-barrier contraception during study for women of childbearing potential

-CONFIDENTIAL- Page 22 of 33

- 8. Willingness to maintain a study diary
- 9. Life expectancy > 3 months
- 10. Written informed consent

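### Overall survival: the plain log-rank test is valid, but it leaves out tumour status, which is already collected and would give a more efficient and stable exploratory comparison at no cost

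*Combined protocol and SAP*

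**What the plan says.** OS is a secondary efficacy endpoint (section 5.2.2): "Overall survival (OS) defined as the time from randomization to death from any cause". Section 5.1.2 lists it both for the main comparison of the bag systems and for A-1 vs A-2. The analysis, in section 6.3.2 under Secondary Endpoints and in the ITT population, is: "For the time-to-event variable OS, the Kaplan-Meier method will be used, and treatment groups will be compared using a log rank test". No strata, covariates, Cox model or hazard ratio are specified. The same section sets the standing of the result: "All resulting p-values for secondary endpoints will be considered descriptive", and "All p-values will be two-sided if not stated otherwise". It also allows methods to be modified after a suitability check and leaves further detail to the SAP, to be fixed at the latest before database lock.

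On the population, section 7.1 admits: "Histologically confirmed metastatic or localized solid tumor. Perioperative setting of HPN is allowed", the last on condition that home PN is planned for at least two months. Section 3.1 describes cancer cachexia as "leading to a very limited prognosis especially in the metastatic situation".

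On randomization, section 4 states: "Patients will be stratified according to ECOG (0-1 vs. 2 vs. 3), the modified Glasgow Prognostic Score (mGPS) (0-1 vs. 2", plus concurrent systemic anti-cancer treatment (yes/no). The same factors are used again for the second randomization within Arm A. Tumour status is not among them. In the analysis section it appears only in the list of baseline descriptors: "Tumor status (localized or metastatic solid tumors". It is not one of the named subgroups in section 6.3.1, although that list is open.

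**The concern.** The protocol itself treats metastatic disease as carrying the worse prognosis, enrols both kinds of patient, and records which is which, but does not use that information in the survival comparison. Two things follow. A log-rank test that pools patients of very different prognosis is less sensitive than one that compares like with like. And if one arm happens to receive more localized patients, the pooled comparison shifts in that arm's favour.

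This matters most for A-1 vs A-2. Section 3.6 says glucose-reduced nutrition can be tested for an inhibitory effect on tumour growth, yet section 5.2.2 lists no response or progression endpoint. OS is therefore the only listed outcome that bears on that idea, with about 72 patients per arm.

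**Working it through.** **Group sizes.** The only powered figure in the plan is for autonomy (section 6.1): 5% vs 20%, 2:1, two-sided 0.05, Walters approximation. With 64 and 128 patients, the continuity-corrected proportions are 0.05 + 1/128 = 0.0578 and 0.20 − 1/256 = 0.1961. The difference of arcsine square roots is 0.4587 − 0.2428 = 0.2159. Multiplying by √(4 × 64 × 128/192) = 13.06 gives 2.82, and Φ(2.82 − 1.96) = 80.5%. The stated 192 is reproduced. With 10% dropout, 64/0.9 rounds up to 72, doubled to 144, total 216. So A vs B is 144 vs 72 and A-1 vs A-2 is 72 vs 72. The plan gives no figure for OS to reproduce.

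**Chance imbalance.** For localized share f, the SD of the difference between arms is √[f(1 − f)(1/n₁ + 1/n₂)]. This ignores any indirect balancing by the existing strata.
- f = 30%, A vs B: √[0.21 × (1/144 + 1/72)] = 6.6 points; two SD = 13 points.
- f = 30%, A-1 vs A-2: √[0.21 × 2/72] = 7.6 points; two SD = 15 points.
- For f from 20% to 50%, a difference of at least 10 points has probability 8–17% (A vs B) and 13–23% (A-1 vs A-2).

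**Efficiency.** Assumptions, none of them in the documents: exponential survival, true hazard ratio 0.65 and the medians shown below. Accrual is uniform over 36 months with cut-off at 48 months (timing taken from section 6.2), with no loss to follow-up and 4,000 simulated trials per row. Power is for a two-sided 0.05 test, used here only as a measure of efficiency.

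| Localized share | Median OS, metastatic/localized (months) | A vs B: plain → stratified | A-1 vs A-2: plain → stratified |
|---|---|---|---|
| 20% | 8/16 (twofold) | 72.5 → 75.7% | 58.6 → 62.2% |
| 40% | 8/16 | 69.5 → 74.1% | 55.9 → 60.1% |
| 20% | 8/24 (threefold) | 67.7 → 75.7% | 52.8 → 60.3% |
| 40% | 8/24 | 58.6 → 69.7% | 46.6 → 56.2% |
| 20% | 6/36 (sixfold) | 54.9 → 76.1% | 44.6 → 62.6% |
| 40% | 6/36 | 44.0 → 69.0% | 33.8 → 57.0% |

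Other settings extend the range slightly. With 15% localized and a twofold gap, adjusting for tumour status gains only 2 points (71 → 73%). With 30% localized and a threefold gap, stratifying gains 12 points (65 → 77% for A vs B; 51 → 63% for A-1 vs A-2). With 40% localized and medians of 6 and 18 months, the gain is just under 13.

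**Validity.** With no treatment effect, both tests reject in 4.3–6.3% of simulated trials. Among those trials with an imbalance of at least 10 points, the plain test rejects in 6–20% (A vs B) and 6–15% (A-1 vs A-2).

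**Shift from imbalance.** With no true effect, each 10 points more localized patients in one arm multiplies that arm's unadjusted hazard ratio by about 0.93 (twofold gap), 0.90 (threefold) or 0.85 (sixfold). For a two-SD imbalance at 30% localized and a threefold gap:
- A vs B: 0.90^1.32 ≈ 0.87, a log shift of 0.139.
- A-1 vs A-2: 0.90^1.53 ≈ 0.85, a log shift of 0.163.

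The smallest possible standard error of the log hazard ratio, if every patient died, is 1/√(216 × 2/3 × 1/3) = 1/√48 = 0.144 for A vs B and 1/√(144/4) = 0.167 for A-1 vs A-2. Both shifts are below one standard error.

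**The case against.** OS is exploratory. Its p-value is declared descriptive, without reference to hypotheses or a significance level, and no OS effect, event count or power is planned. In that sense no planned power is lost. This stands, and it limits the weight of the point. An exploratory endpoint is still read through its estimate, however, and the plan commits to no OS effect estimate at all.

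A reader might infer that the plain test inflates false positives. It does not: overall type I error is preserved, and that 5% already includes the unlucky allocations. Only the result conditional on an imbalance is affected.

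A reader might also infer that nothing balances tumour status. That goes too far. ECOG, mGPS and concurrent systemic treatment are randomization strata and may balance it in part where they track disease extent. None of them records it directly.

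An unadjusted hazard ratio nearer 1 than the within-stratum one is not an error either. The two are different quantities (non-collapsibility), and the plain log-rank test matches the pooled Kaplan-Meier curves.

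Finally, section 6.3.2 leaves room for modified methods and further SAP detail, and an imbalance would show in the baseline table. That makes this a matter the SAP could settle, but the present text commits to nothing. A chance imbalance does not make a log-rank test unsuitable, so the modification clause need not be triggered. In an open-label trial, a covariate chosen after the imbalance has been seen is less convincing than one named beforehand.

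**Conclusion.** The point holds as a missed, essentially free improvement to an exploratory endpoint. The survival test is valid, but it ignores a prognostic variable that the protocol recognises and collects.

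The size cannot be fixed from the documents, because the localized share, the prognostic gap and the OS effect are all assumed. At a true hazard ratio of 0.65 the gain is small for a twofold gap (about 2–5 points of power), moderate for threefold (8–13) and larger for wider gaps (18–25 for sixfold). The documents do not show how wide the gap is among patients who all need PN and have a life expectancy above three months. The distortion from a fairly extreme imbalance stays within one standard error in the 30%, threefold case.

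The documents do not support reading this as a flaw that invalidates the OS comparison, nor as one that touches the autonomy analysis or the sample size of 216.

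**What to change.** In section 6.3.2, for both A vs B and A-1 vs A-2:
- Prespecify a log-rank test stratified by baseline tumour status (localized vs metastatic).
- Report a Cox hazard ratio with 95% confidence interval, stratified by tumour status and adjusted for ECOG, mGPS and concurrent systemic anti-cancer treatment as covariates.
- Do not cross all factors as strata. The randomization factors form 3 × 2 × 2 = 12 cells and tumour status doubles this to 24, an average of 216/24 = 9 patients per cell, or 144/24 = 6 for A-1 vs A-2.
- Keep the Kaplan-Meier curves and the unstratified log-rank test as supporting results.

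The cost is a sentence or two in the protocol or SAP, written before any OS data are examined. All the variables are already collected, so no new data, visits or patients are needed.

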#### 7 Patient Selection

#### 7.1 Inclusion Criteria

Patients\* must meet the following criteria to be eligible for the study:

- 1. Age  $\geq$  18 years
- 2. Histologically confirmed metastatic or localized solid tumor. Perioperative setting of HPN is allowed if HPN is planned for a duration of  $\geq 2$  months
- 3. ECOG performance status of 0, 1, 2 or 3
- 4. Indication for PN (the subject needs a PN independent of the trial)
- 5. PN planned for 3 or more days per week
- 6. Negative pregnancy test in women of childbearing potential
- 7. Willingness to perform double-barrier contraception during study for women of childbearing potential

-CONFIDENTIAL- Page 22 of 33

- 8. Willingness to maintain a study diary
- 9. Life expectancy > 3 months
- 10. Written informed consent

#### 7.2 Exclusion Criteria

Patients who meet any of the following criteria will be excluded from study entry:

- 1. > 4 weeks of consecutive (3  $\ge$  days per week) parenteral nutrition in the last 3 months prior to study enrolment
- 2. Participation in another interventional clinical trial that could influence the endpoints of this trial or planned participation in such a study at the same time as this study is active (participation in other trials is possible in the follow up time for OS). The study is active, if the patients receive study treatment (PN), did not discontinue the trial for other reasons, and is still within the 12 months active study period
- 3. Current catheter related infection at baseline. In patients with a suspected/proven previous conservatively managed catheter-related infection, a negative pair of blood cultures drawn from the central catheter is required.
- 4. Pregnancy or breastfeeding
- 5. Known hypertriglyceridemia ≥ CTCAE grade 3
- 6. Unable or unwilling to provide written informed consent and to comply with the study protocol
- 7. Uncontrolled diabetes mellitus
- 8. Congestive heart failure NYHA  $\geq$  3
- 9. Renal insufficiency GFR < 30 ml/min
- 10. Uncontrolled infection
- 11. Liver insufficiency

### 8 Therapy scheme

The S3-Guideline of the German Society for Nutritional Medicine for Clinical Nutrition in Oncology should be used as guidance when setting-up the PN therapy plan [S3-Guideline of the German Society for Nutritional Medicine (DGEM) in Cooperation with the DGHO, the ASORS and the AKE, Clinical Nutrition in Oncology].

The following must always be considered before determining the patient's therapy scheme:

• For all treatment arms the composition of the nutrients can differ from the tables below due to site-specific routine or investigator's/medical decision.

-CONFIDENTIAL- Page 23 of 33

\*There are no data that indicate special gender distribution. Therefore, patients will be enrolled in the study gender-independently.

- The frequency of PN is not pre-determined for any treatment arm and can change during the course of the study based on the evolving nutritional status of the patient.
- The recommended infusion duration is 12-14 hours. However, the duration can differ and the maximum infusion speed per macronutrient should always be considered.
- If the run-in phase was not conducted at the inpatient facility, then a low energy nutrition should be considered for the start of HPN to avoid a refeeding syndrome.
- For Arm A-1 and Arm A-2 some modifications to the initially considered therapy plan
  might become necessary based on to the randomization results. These modifications
  should only be done if medically acceptable.

Note: Any existent clinical contraindications must always be of overriding importance compared to the randomization results and therapy as randomized should only be administered if medically acceptable.

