#### Arm A-1: Standard Low Glucose Parenteral Nutrition using Eurotubes®.

Patients randomized to Arm A and in a second randomization to treatment Arm A-1 receive PN reduced in glucose in Eurotubes®.

or

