#### Arm A-1: Standard Low Glucose Parenteral Nutrition using Eurotubes®

Patients randomized to treatment Arm A-1 will receive PN reduced in glucose in Eurotubes® (Eurozyto).

The following displays a guidance for the PN composition administered in Arm A-1. The amounts listed are understood as daily dose. Underlying medical conditions, intolerance etc. must always be considered per individual patient.

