#### Macronutrients:

For the macronutrients, body weight is understood as the ideal body weight for the patient according to a BMI of 19 - 24 for women and 20 - 25 for men.

Glucose: 1.0 - < 2.0 g per kg body weight

Amino acids: 1.2 - 1.5 g per kg body weight

Lipids: 0.5 - 2.0 g per kg body weight

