#### Arm A-2: Standard Parenteral Nutrition using Eurotubes®

Patients randomized to treatment Arm A-2 will receive standard PN in Eurotubes® (Eurozyto).

The following displays the specifications for the PN composition administered in Arm A-2. The amounts listed are understood as daily dose. Underlying medical conditions, intolerance etc. must always be considered per individual patient.

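### Section 8 lets site routine alone take glucose outside the A-1 or A-2 range, although glucose is the only specified component that separates these two randomised arms

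*Combined protocol and SAP*

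**What the plan says.** Arm A is randomised a second time, 1:1, to A-1 or A-2 (section 4). The A-1 paragraph there states the intent: "Patients randomized to Arm A and in a second randomization to treatment Arm A-1 receive PN reduced in glucose". Section 8 gives a daily composition table for each arm. For A-1 the entry is "Glucose: 1.0 - < 2.0 g per kg body weight"; for A-2 it is 2.0 to 4.0 g/kg. Both are per kg of ideal body weight.

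Four statements in section 8 govern departures from these tables:

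- First bullet: "For all treatment arms the composition of the nutrients can differ from the tables below due to site-specific routine or investigator's/medical decision".
- Fourth bullet: where there was no inpatient run-in, "low energy nutrition should be considered for the start of HPN to avoid a refeeding syndrome".
- Last bullet: it begins "For Arm A-1 and Arm A-2 some modifications to the initially considered therapy plan", ties these changes to the result of the randomisation, and allows them only where medically acceptable.
- Closing note: "therapy as randomized should only be administered if medically acceptable", with clinical contraindications placed above the randomisation result.

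The tables are introduced with different force. For A-1: "The following displays a guidance for the PN composition administered in Arm A-1". For A-2: "The following displays the specifications for the PN composition administered in Arm A-2". The text after each table has the investigator set the composition by site routine while taking the listed values into account.

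**The concern.** The second randomisation exists to study reduced glucose, which section 3.1 lists among the unresolved problems and section 3.6 says can be tested. A site that prescribes 2.0 g/kg or more to an A-1 patient because that is its habit, or less than 2.0 g/kg to an A-2 patient, complies with the first bullet. The patient nevertheless receives the other sub-arm's glucose. Enough such prescriptions would make the sub-arms alike in the one factor that was assigned. A finding of no difference could then reflect either no effect of glucose or too little separation in glucose. Recording the therapy plan, as section 4 and note 14 of Table 1 require, can reveal a crossing but does not prevent it.

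**Working it through.** **1. What separates A-1 from A-2.** Comparing the two tables in section 8 line by line:

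| Component | A-1 | A-2 |
|---|---|---|
| Bag system | Eurotubes | Eurotubes |
| Glucose, g/kg | 1.0 to <2.0 | 2.0 to 4.0 |
| Amino acids, g/kg | 1.2–1.5 | 1.2–1.5 |
| Lipids, g/kg | 0.5–2.0 | 0.5–2.0 |
| Electrolytes, trace elements, vitamins, water | same | same |
| Volume, ml/kg | 30–40 | 30–40 |
| Energy, kcal/kg | 25–30 | 25–30 |

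Only glucose differs. The ranges do not overlap, but they meet at 2.0 g/kg. This concerns specified ranges; in practice lipids may rise when glucose falls.

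**2. Does the energy target force glucose out of range?** With the protocol's factors (4, 4 and 10 kcal per g of glucose, amino acids and lipids):

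- A-1: 4×1.0 + 4×1.2 + 10×0.5 = 13.8, up to just under 4×2.0 + 4×1.5 + 10×2.0 = 34 kcal/kg.
- A-2: 4×2.0 + 4×1.2 + 10×0.5 = 17.8, up to 4×4.0 + 4×1.5 + 10×2.0 = 42 kcal/kg.

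The 25–30 target fits inside both, so it gives no reason to cross.

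**3. Which analyses are exposed.** Section 6.3.2 puts secondary endpoints on the ITT population, except safety (safety set) and CRI (per protocol). Section 6.3.1 assigns both of those sets by treatment actually given, and per protocol also requires home PN in line with the arm. Neither definition gives a glucose limit. Dilution therefore follows directly for weight, CRP, albumin, OS and QoL. For CRI and safety it depends on how treatment actually given is applied to glucose.

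**4. Size of the sub-arms.** Section 6.1 plans 128 + 64 = 192 patients for the primary test. The Walters approximation at 5% versus 20% reproduces this (power 0.805; 126 + 63 gives 0.798). Of the 216 enrolled, 216 × 2/3 = 144 go to Arm A, and 144/2 = 72 to each sub-arm. The protocol gives no power figure for A-1 versus A-2.

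**5. Illustration of dilution.** The documents give no crossing rate. Assume mid-range prescribing (1.5 and 3.0 g/kg), crossing by a share f of A-1 only, crossers receiving x g/kg, and an effect linear in dose. Then:

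- contrast = 3.0 − [(1 − f)×1.5 + f×x]
- share retained r = contrast/1.5
- equivalent patients per sub-arm = 72×r²

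| f (A-1 patients) | x | Contrast | r | Equivalent n |
|---|---|---|---|---|
| 10% (about 7) | 2.1 | 1.44 | 0.96 | 66 |
| 10% | 3.0 | 1.35 | 0.90 | 58 |
| 20% (about 14) | 2.1 | 1.38 | 0.92 | 61 |
| 20% | 3.0 | 1.20 | 0.80 | 46 |
| 40% (about 29) | 2.1 | 1.26 | 0.84 | 51 |
| 40% | 3.0 | 0.90 | 0.60 | 26 |

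If instead a share f in each sub-arm received the other's typical dose, r = 1 − 2f: 0.80, 0.60 and 0.40 at f = 10%, 20% and 30%. The documents cannot choose between these cases.

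**6. The weight behind g/kg.** Ideal weight may correspond to BMI 19–24 (women) or 20–25 (men). At a given height the permitted weights span 24/19 = 1.26 or 25/20 = 1.25. A daily dose equal to 2.1 g/kg at the lower weight is 2.1/1.26 ≈ 1.66 or 2.1/1.25 = 1.68 g/kg at the upper. A near-cut crossing can thus be made compliant by choosing another permitted weight.

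**The case against.** The strongest reply is that section 8 should be read as a whole. The first bullet is general, while the text on A-1 and A-2 is specific: A-1 gets reduced glucose, the randomisation result changes the plan first considered, and only medical grounds excuse departure from assigned therapy. On that reading routine governs the nutrients that do not define the arms, assignment governs glucose, and all that is missing is a cross-reference. The reply establishes the intent. It does not remove the permission, because the first bullet names routine as a separate ground in every arm, and the later statements neither limit it nor mention it.

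Other parts of the opposing case stand and limit the point:

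- **Direction.** A reader might infer that crossing runs only upward from A-1, because Arm B follows site routine and its glucose range equals that of A-2. No section reports any site's actual glucose routine, and the Arm B range is itself only guidance, so this remains an assumption.
- **Breadth.** A reader might infer that every A-1 versus A-2 comparison is diluted. The analysis sets support that directly only for the ITT endpoints.
- **Exposure.** The figures are per PN day. Frequency is not fixed by section 8 and may be as low as 3 days a week under inclusion criterion 5, so they do not measure total glucose exposure.
- **Monitoring.** Plans and their changes are recorded, and section 6.3 has major violations listed, with handling left to the SAP. The eCRF fields are not shown, so it cannot be said that adherence would go unseen.

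Flexibility for individual patients is proper in this population. That argues for keeping the medical exception, not for accepting routine as a ground to change the assigned factor.

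**Conclusion.** The point holds. As written, a site can follow section 8 and, for routine reasons alone, give an A-1 patient glucose in the A-2 range or the reverse. This is in tension with the protocol's own statements of intent.

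The size is unknown. Crossing rate, crossing dose, direction, mid-range prescribing and linearity are all assumptions; few or near-cut crossings cost little, while frequent or large ones would cost a good deal.

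Two stronger readings are tempting and are not supported. One is that the sub-arms are undefined: their ranges are stated and do not overlap. The other is that the trial's main conclusion is at risk: the primary test compares A with B on autonomy, and the A-1 versus A-2 comparisons are secondary with descriptive p-values. This is a cheap improvement worth making to protect the question behind the second randomisation.

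**What to change.** Add to section 8:

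> In Arms A-1 and A-2, prescribed daily glucose must stay on the assigned arm's side of 2.0 g/kg ideal body weight unless there is a documented medical reason (including a low-energy start to avoid refeeding syndrome). Site-specific routine alone is not such a reason.

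Keep the tables and the medical exception as they are. Set each patient's ideal body weight once, before the second randomisation, and use it for all later prescriptions; this closes the gap left by the permitted BMI span. In the SAP, add one descriptive table giving, by arm and visit, the share of A-1 and A-2 patients whose prescribed glucose is on the assigned side.

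Cost: sites must note a medical reason when a prescription crosses the cut, and up to two eCRF fields (daily glucose and the ideal weight) may be needed if the therapy plan does not already hold them. Sample size and randomisation ratios do not change. Prescribing close to the cut, such as 1.9 versus 2.0 g/kg, stays possible, so the change limits crossing but does not guarantee a wide contrast.
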